Lichen sclerosus (LS) is a chronic, inflammatory skin disorder of genital and extragenital skin.¹ It most commonly affects the anogenital region of adult women.² Lichen sclerosus (LS) was described for the first time in 1887. Since then, many synonyms have been in use, notably 'Kraurosis vulvae,' 'vulvar dystrophy,' 'white spot disease,' and 'lichen sclerosus et atrophicus' or 'guttate scleroderma.¹ All of these terms have been abandoned and replaced by 'lichen sclerosus,' which is now used for genital and extragenital lesions.¹ LS is a chronically relapsing disease with a potential for atrophy, destructive scarring, functional impairment, and malignant evolution.^{1,3,4} Therefore, early diagnosis, prompt treatment, and long-term follow-up of affected patients are mandatory.¹

It is estimated that up to 20% of all women will experience significant vulvar symptoms at some point in their lifetime.² Although women's health is a topic of growing concern in today's society, conditions such as vulvar lichen sclerosus (VLS) are often underdiagnosed and undertreated. Most cases are diagnosed in postmenopausal women.⁵ The involved skin becomes thin and white, with frequently present bruises or petechiae and anatomic changes. Symptoms include persistent itching and soreness or burning. At advanced stages of lichen sclerosus, scarring after inflammation may lead to severe damage by fusion of the labia, narrowing of the vaginal opening, burying of the clitoris in women and girls and risk of developing squamous cell carcinoma.

The treatment of VLS aims at controlling the symptoms, stopping further scarring and distortion and reducing the risk of cancer. Previously, the gold standard in treatment was ultra-potent topical steroids (i.e. clobetasol propionate).⁵ Currently, mid to high-potent topical steroids are a first-line therapy. The anti-inflammatory properties of clobetasol and other steroids have been most effective in managing associated symptoms, decreasing inflammation, and preventing progression of the condition and subsequent scarring.⁶ Second-line treatments include calcineurin inhibitors, retinoids, and immunosuppressors. Surgery is used only for the treatment of complications associated with VLS.⁵

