Contemporary VLS treatment modalities suffer from dependence on long-term patient compliance and high recurrence rates. The fractional carbon dioxide laser (CO₂) has been applied to treat skin disorders⁷ and to induce vaginal rejuvenation⁸, reconstitute normal vaginal flora⁹ and to drive collagenogenesis tissue remodelling.¹⁰ Although topical steroids are the gold standard treatment for VLS, fractional CO₂ resurfacing was successful in achieving remission for severe, hyperkeratotic VLS not responding to super-potent topical corticosteroids. In these patients, VLS was subsequently able to be maintained with topical corticosteroid treatment.¹⁰

The histological changes and relief of vaginal symptoms, such as itching and dryness, elicited with fractional CO₂ technology justify testing it as an alternative and/or adjunctive treatment for VLS. This clinical research will evaluate treatment efficacy of the CO₂RE CO₂ laser device with the External Intima fractional handpiece for improving the clinical signs of VLS and relieving symptoms associated with this condition.

CO₂RE Device Description

The CO₂RE laser system (Figure 1) utilizes a sealed-off, metal carbon dioxide gas tube that is radiofrequency (RF)-excited and air-cooled, emitting light at a wavelength of 10.6 µm with

programmable pulse duration and frequency. The system has a programmable 2-axis scanning laser beam device that allows the physician to select the skin area coverage from a selection of predetermined patterns in different sizes based on the skin area to be treated. The versatility of the fractional CO₂RE system enables precise, effective and simultaneous treatment of the skin's surface in the middle and deep dermal levels. The CO₂RE system consists of a treatment component and an internal control component. The treatment component consists of the laser delivery handpiece. A computer with a touch screen keyboard also provides controls for the fractionated delivery of the 10.6 μ m beam.

Figure 1: CO₂RE device

In this study, the external fractional handpiece (Figure 2) will be used to perform treatments to the vulvar area affected by lichen sclerosus.

Figure 2: CO₂RE Intima External Handpiece

INTENDED USE IN GYNECOLOGY

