Change from baseline in presence and severity of symptoms (5-point severity scale), clinical signs (3-point severity scale) and architectural changes (3-point severity scale) at the 6-week, 3-month, 6-month and 12-month follow-up visits. (**Appendices I & II**).

Secondary Safety Endpoints

Evaluate the safety of the treatment:

1. Clinical evaluation of treated area at each study visit. Clinical photography will be performed for study documentation (**Appendix IV**).
2. Pain/discomfort level using a 10-point Numerical Scale Response (NSR) after each treatment (**Appendix V**).
3. Number, severity and type of adverse events recorded throughout course of the study.
4. 1 week ± 2 days post first treatment safety phone call (review of 1-week patient diary) – (**Appendix VI**).

Secondary Efficacy Endpoints

1. Sexual function, using the Female Sexual Function Index (**Appendix III**), at baseline and at the 3-month and 6-month follow-ups. *An overall score ≤ 26.55 is classified as Female Sexual Disorder (FSD).*¹⁵
2. Histological signs (degree of hyperkeratosis, epidermal atrophy and dermal inflammation) at baseline and at 6 weeks and 6 months after the final treatment.
3. Subject satisfaction, using a 5-point Likert scale (-2=very dissatisfied; 2=Very satisfied), will be assessed at the 6-week, 3-month, 6-month and 12-month follow-up visits (**Appendix VII**).

SUBJECT POPULATION

Up to 45 female subjects who meet the following inclusion / exclusion criteria may be enrolled.

Subject Withdrawal and Replacement

Subjects enrolled in the study can discontinue their participation at any time for any reason without prejudice or reduction in the quality of their medical care. The investigator or sponsor can terminate a subject's participation in this study to protect the subject's health or if the subject fails to follow directions resulting in noncompliance to study procedures. Subjects who withdraw or are terminated from the study may be replaced to allow up to 45 subjects to complete the study. Subjects who fail to complete the treatment will be replaced and will not be evaluable.

Inclusion Criteria

1. Able to read, understand and sign informed consent for study participation;
2. Female subjects with age 18-80 years;
3. Biopsy demonstrates biopsy-proven lichen sclerosus and/or there are characteristic changes for vulvar lichen sclerosus on physical examination;

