4. Treatment of LS has been recalcitrant to mid to high-potent topical corticosteroid treatment or subject refuses topical corticosteroid treatment. Recalcitrance to therapy is defined as no response to topical corticosteroids of an adequate potency (i.e. clobetasol propionate 0.05% ointment or other steroids) and a sufficient duration (12 weeks of use) or lack of symptomatic control of the disease with a maintenance therapy;
5. Topical corticosteroid treatment, if any, will be continued during the study period;
6. Exogenous hormone treatment, if any, will be continued during the study period (type and dose must stay consistent throughout the study);

7. One or more of the following symptoms: itch; pain unrelated to intercourse; pain, skin tearing or bleeding with intercourse; changes/decrease in sexual function;
8. Characteristic changes for vulvar lichen sclerosus on physical examination;
9. No breaks, tears or lesions, malodorous discharge or strawberry cervix present on gynecological exam.

Exclusion Criteria

1. Presence of clinically atypical appearing nevi in the area to be treated;
2. Unexplained vaginal bleeding;
3. Active infection, specifically: urinary tract infection, vulvar or vaginal infection (candidiasis, genital herpes/HSV, bacterial vaginosis, trichomonas);
4. History of vulvar or any gynecological malignancy, as well as history of pelvic radiation therapy or stem cell transplant;
5. Pelvic organ prolapse > stage 2;
6. Pregnancy or planning pregnancy during the study;
7. Systemic treatment with immuno-modulatory drugs.
8. Use of vaginal dilators during study.

STUDY PROCEDURES

Enrollment and Screening

During the first visit, the investigator will screen the subject for eligibility to participate in the clinical study. The inclusion/exclusion criteria will be reviewed, the subject's medical history, an examination of the subject's treatment areas will be conducted.

The subject will review the informed consent form (ICF) and the study will be explained to the subject including all risks, potential benefits, procedures, visit requirements, and other alternative treatment options. If the subject qualifies and wishes to participate they will complete the ICF with a signature and date. The original will be retained with subject's records and a copy will be provided to the subject.

The following measurements will be performed and recorded at the specified times throughout the study (as specified in Error! Reference source not found.).

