Table 2. Study Measurements

Assessment	When to conduct	Method
Complete the Inform Consent form and Eligibility Screening and Medical History	During the screening visit / prior to the 1 st treatment	Physician or staff will complete the form with the study subject
PAP smear if not up-to-date (within 3 years according to ACOG guidelines)		Patient should provide lab results of up-to-date normal cell cytology
Urine pregnancy test for women capable of becoming pregnant		Patient should have a negative pregnancy test
Gynecological exam		Physician will examine the vulvar and vaginal area for any signs of active infection or atypical nevi
Vulvar biopsy of treatment area (optional)	Prior to the 1 st treatment and at the 6-week and 6-month follow-ups	Biopsies will be obtained from up to 10 subjects to conduct histological assessment. Lab reports will be provided to show changes in markers compared to baseline.
Subject assessment of symptoms	
 • Baseline or pre-Tx. 1 • At the 6-week, 3-month, 6-month and 12-month follow-up visits 	Subjects will complete the Symptom Severity Questionnaire, according to the pre-defined scales (Appendix I)
Physician assessment	
 • Baseline or pre-Tx. 1 • Prior to treatments • At the 6-week, 3-month, 6-month and 12-month follow-up visits 	Physician will assess clinical signs associated with VLS, according to the pre-defined scales (Appendix II)
Subject assessment of sexual function	
 • Baseline or pre-Tx. 1 • At the 3-month and 6-month follow-up visits 	Subjects will complete the Female Sexual Function Index (FSFI) – Appendix III
Clinical evaluation and photographs of treated area	
 • Baseline or pre-Tx. 1 • Prior to treatments • At the 6-week, 3-month, 6-month and 12-month follow-up visits 	Physician will evaluate the treatment area. Physician or staff will take photographs of the treatment area (Appendix IV)
Treatment pain assessment	Immediately after each treatment	NSR Scale (Appendix V)
Subject 1-week daily diary - reviewed at the 1wk FU after the first treatment	The daily diary will be provided at the 1 st treatment visit and reviewed by phone during the 1-week safety evaluation	Subjects will be requested to complete a daily diary with data regarding their comfort, AE, and activity (7 days of follow-up post 1st treatment) – Appendix VI

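### Background topical steroid must be continued but not held constant, and no medication review is listed at any treatment visit

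*Protocol*

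**What the plan says.** **Eligibility (Protocol, Inclusion and Exclusion Criteria).** Item 5: "Topical corticosteroid treatment, if any, will be continued during the study period". Item 6 makes the same demand for exogenous hormones and adds "type and dose must stay consistent throughout the study". Item 4 admits women with no response to 12 weeks of adequate topical steroid and women not controlled on maintenance therapy. It also admits a third group: "or subject refuses topical corticosteroid treatment". The only exclusion on disease-modifying drugs is item 7, "Systemic treatment with immuno-modulatory drugs".

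**Medication recording.** Screening takes a list of all medicines used in the previous 6 months (Screening / Initial Evaluation and Baseline, item 3). The Follow-up Visits section lists a review of medication changes since the last visit, at 6 weeks and at 3, 6 and 12 months. No medication review appears under Prior to Each Treatment Procedure, in the treatment and post-treatment steps, or as a row of Table 2. The one-week diary collects "data regarding their comfort, AE, and activity".

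**Role of steroid and laser (Background).** Steroids "have been most effective in managing associated symptoms, decreasing inflammation, and preventing progression of the condition and subsequent scarring". The evidence on the laser is said to "justify testing it as an alternative and/or adjunctive treatment for VLS".

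**Design and endpoint.** There is one non-randomized group. The primary endpoint is the change from baseline in symptoms, clinical signs and architectural changes at the four follow-up visits.

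**The concern.** Without a control group, anything that changes alongside the laser course becomes part of the measured change from baseline. Topical steroid is the obvious candidate, because the protocol itself credits it with acting on symptoms and inflammation. A start or step-up could flatter the laser, and a reduction could mask it. For architectural change the link is weaker: the protocol credits steroids with preventing scarring, not with reversing it.

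Testing the laser as an adjunct is a legitimate aim, but it needs a background regimen that is either stable or known. As written, item 5 does not make it stable, and the listed procedures do not make it known during the treatment course. The Treatment Visits paragraph under Data Analysis also compares clinical signs from those visits with baseline to assess efficacy, so efficacy data are gathered at visits with no listed check on concurrent topical therapy.

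**Working it through.** The protocol states no figure on this point, so there is none to reproduce. The check is a comparison of texts plus visit-schedule arithmetic.

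**1. Item 5 against item 6.** The items are adjacent and both require continuation. Only item 6 adds constancy of type and dose. Stopping steroid would breach item 5; changing potency or frequency would not clearly do so. Because item 6 spells the condition out, it is hard to read continuation in item 5 as meaning an unchanged regimen. Neither item, nor exclusion 7, covers starting a topical agent.

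**2. Where medication is listed.** For a subject with five treatments and a separate screening day:
- visits: 1 screening + 5 treatments + 4 follow-ups = 10, which agrees with the maximum of 10 visits under Payment for Participation;
- visits with medication listed: 1 + 4 = 5 of 10;
- treatment visits with medication listed: 0 of 5.

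**3. Time to the first listed review after screening.** Inputs: up to 5 treatments at 4 ± 1-week intervals (Synopsis, Treatment Duration), and the first follow-up at 6 ± 2 weeks after the last treatment (Follow-up Visits).
- Course length = (5 − 1) × 4 = 16 weeks; range 4 × 3 = 12 to 4 × 5 = 20.
- Treatment 1 to the 6-week visit = 16 + 6 = 22 weeks; range 12 + 4 = 16 to 20 + 8 = 28.

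Even the shortest of these, 16 weeks, exceeds the 12 weeks that item 4 treats as enough to assess response to steroid. Fewer than five treatments would shorten the gap.

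**4. What the 6-week review covers.** If the last visit means the final treatment, changes between treatments 1 and 5 fall in no listed review. If it means the last recorded medication list, which is the more natural reading, the review covers the whole course in retrospect, up to 28 weeks after treatment 1.

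**5. Whether adverse event reporting fills the gap.** Table 2 has adverse event interviews before and after each treatment. The wording on what must be recorded points both ways:
- *Broad:* the opening definition takes in any adverse change in health during participation, the relationship categories include unrelated events, and the action taken must be described.
- *Narrow:* the text under Anticipated Adverse Effects defines an event by its relation to the device or study procedures, and has disease progression recorded where the investigator attributes it to the device.

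A flare leading to a step-up may therefore be recorded, but the text does not ensure it. A change made without any adverse event has no route here at all.

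**The case against.** **Some capture exists.** Screening medicines are recorded, changes are reviewed at all four follow-up visits, and adverse events are asked about at every treatment. Case report form entries must match the clinic chart, and a prescription change by the treating clinic would normally be charted. The forms are not shown and may have a medication field. This stands, so a reader should not infer that changes during the course go wholly unrecorded. It does not close the gap, because actual application frequency is unlikely to be charted and the adverse event wording is inconsistent.

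**Eligibility limits the bias.** Women with no response to 12 weeks of adequate steroid have little to gain from a step-up, and refusers are the least likely to start. This largely stands and leaves women on maintenance therapy as the main exposed group. It is not a full answer: refusers need not have failed steroid, and the Background cites patients whose disease could be maintained on topical steroid after fractional CO₂ treatment, so steroid use after laser is foreseeable.

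**The weeks do not measure bias.** This stands. The 22 weeks describe the visit schedule. A reader might take the length of the gap as a measure of distortion, or conclude that the laser result is inflated. The document gives no frequency of steroid changes and no effect size, so it supports neither inference.

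**Analysis belongs elsewhere.** One might want assessments after a step-up scored as no improvement. That is a debatable way of handling an intercurrent event and is a matter for the statistical analysis plan, which is not shown. The eligibility wording and the visit procedures are protocol matters, and no analysis plan can restore steroid data that were not collected.

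**Conclusion.** The point holds as a gap in drafting and data collection. Item 5 does not hold background topical steroid constant, starting a topical agent is not addressed, and no treatment visit has a listed medication review. With five treatments at nominal spacing, the first listed review after screening comes 22 weeks after treatment 1 (16 to 28 across the visit windows).

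In a single-arm study judged on change from baseline, steroid changes in that period mix with the laser effect on symptoms and clinical signs, and less clearly on architectural change. The size and direction of any bias cannot be derived from the document.

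The conclusion assumes that the listed procedures are what sites will follow and that the unseen forms add no systematic medication record at treatment visits. If they do, the recording part falls away and the wording of item 5 remains. Closing the gap would not remove the other limits of an uncontrolled design, and the point is no argument against adjunctive use.

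**What to change.** 1. Extend item 5: type, potency and frequency of topical steroid are to be held constant from baseline, and no new topical VLS agent is to be started unless clinically needed, with any change recorded.
2. Add one line under Prior to Each Treatment Procedure to record topical VLS agent, potency and weekly frequency. Make the same record at baseline and at each follow-up visit.
3. Report by visit the number of subjects who started, increased or reduced topical therapy.

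The clinical-need exception still permits step-ups, so most of the gain comes from the recording. Any sensitivity analysis that uses these data is left to the statistical analysis plan.

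Cost: one case report form line per visit, a simple table of counts, and a slightly tighter restriction on background therapy. No visit, procedure or subject is added.

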The CO₂RE system device is FDA-cleared under a 510(k) K151655 - intended for laser incision, excision, ablation, and/or vaporization of soft tissue in gynecology (GYN) for the treatment of: conization of the cervix, including cervical intra-epithelial neoplasia (CIN) and vulvar and vaginal intra-epithelial neoplasia (VIN, VAIN); condyloma acuminata, including cervical, genital, vulvar, perineal, and Bowen's disease (Erythroplasia of Queyrat) and Bowenoid papulosa (BP) lesions; and leukoplakia (vulvar dystrophies).

STUDY DESIGN

Study Duration and Timelines

This study is a prospective, non-randomized, single group assignment, interventional clinical trial to evaluate the CO₂RE laser device for safety and efficacy for vulvar lichen sclerosus (vulvar dystrophy) treatment.

Up to a total of 45 female candidates, seeking treatment for vulvar lichen sclerosus from the participating investigator will be enrolled at a participating study site. Subjects will receive up to five (5) CO₂RE treatments.

A 1-week post first treatment safety call will be performed by a study nurse to review the patient daily diary.

Each subject will be followed for 4 additional post treatment visits (FU visits) that will be conducted at:

- 6 weeks post last treatment – 6wk FU ± 2 weeks (Efficacy & Safety).
- 3 months post last treatment – 3m FU ± 2 weeks (Efficacy & Safety).
- 6 months post last treatment – 6m FU ± 2 weeks (Efficacy & Safety).

- 12 months post last treatment – 12m FU ± 2 weeks (Efficacy & Safety).

STUDY OBJECTIVES AND END POINTS

Primary Objective

To evaluate the efficacy of a series of CO₂RE treatments to improve the symptoms, clinical signs, and architectural changes associated with vulvar lichen sclerosus, at 6 weeks, 3 months, 6 months and 12 months after the final treatment.

Secondary Objectives

1. Evaluate sexual function at the 3-month and 6-month follow-ups compared to baseline.
2. Evaluate histological markers at the 6-week and 6-month follow-up compared to baseline.
3. Evaluate discomfort following each treatment.
4. Evaluate the safety of CO₂RE treatments for VLS during the study.
5. Evaluate subject satisfaction at the 6-week, 3-month, 6-month and 12-month follow-up visits.

Primary Endpoint

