Subject satisfaction rating	At the 6-week, 3-month, 6-month and 12-month follow-up visits	Subject will complete the Subject Satisfaction Questionnaire, according to the pre-defined scale – Appendix VII
Adverse Events and Serious Adverse Events	During the entire study period: prior to and immediately after the treatments, during all follow-up visits, and whenever a safety concern is reported by the subject	Examination of the treated area, interview subjects for Adverse Events

Pre-Treatment Procedures

Screening procedures may be conducted on a separate day prior to the 1st treatment, but preferably within 2 weeks.

Screening / Initial Evaluation and Baseline

1. ICF - Prior to any study procedures, written informed consent will be obtained. Once the subject fully understands the possible benefits and risks of the study, the subject will be asked to sign and date the informed consent form (ICF). The subject will be given a copy of the signed ICF.
2. Subject ID - Prior to treatment, the subjects will be assigned a study subject number.
3. Medical History - A medical history will be obtained to determine if the subject meets the study criteria, including a list of all prescribed and over-the-counter medications taken within the previous 6 months will be recorded.
4. PAP smear – each patient should provide up-to-date results of PAP smear with normal cell cytology.
5. Gynecological exam – The study physician will examine the vulvar and vaginal area for any signs of active infection, atypical nevi, or breaks, tears or lesions.
6. Urinalysis - Negative urine pregnancy test for women capable of becoming pregnant.
7. Patients will complete questionnaires (Subject assessment of symptoms & FSFI).
8. For up to 10 subjects, a vulvar biopsy will be taken at baseline.

Vulvar Biopsy Procedure

For subjects participating in the biopsy subset of the study, a punch, or scissor snip, biopsy will be obtained prior to the first treatment and again at the 6-week and 6-month follow up visits. The study patient should be informed on the benefits and risks of the procedure and written consent obtained. The risks include pain, bleeding, infection, scarring, inadequate sample possibly requiring another biopsy procedure, or allergic reaction to anesthetic.

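### Inclusion criteria 5 and 6 require no stable steroid or hormone regimen before baseline, so a recent change in therapy could be confounded with the laser effect, in either direction

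*Protocol*

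**What the plan says.** Three items of the Inclusion Criteria (Subject Population) govern background therapy.

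- Item 4, on steroid history: "Treatment of LS has been recalcitrant to mid to high-potent topical corticosteroid treatment or subject refuses topical corticosteroid treatment". Recalcitrance means no response to a steroid of adequate potency over "a sufficient duration (12 weeks of use" weeks' standard given there, or failure to control symptoms on maintenance therapy, for which no minimum duration is stated.
- Item 5, on steroids during the study: "Topical corticosteroid treatment, if any, will be continued during the study period".
- Item 6, on hormones during the study: "Exogenous hormone treatment, if any, will be continued during the study period (type and dose must stay consistent throughout the study".

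The Exclusion Criteria contain no washout or recent-change rule for either therapy. Item 3 of Screening / Initial Evaluation and Baseline takes a medical history in order to establish eligibility, and as part of it "a list of all prescribed and over-the-counter medications taken within the previous 6 months will be recorded". Under Follow-up Visits, later visits review medication changes since the preceding visit.

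Study Duration and Timelines describes a "prospective, non-randomized, single group assignment, interventional clinical trial". The primary endpoint begins "Change from baseline in presence and severity of symptoms (5-point severity scale), clinical signs (3-point severity scale" and goes on to architectural changes, read at 6 weeks, 3, 6 and 12 months after the last treatment.

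**The concern.** In a one-group study, the change from baseline contains everything that moves the outcome after the baseline reading. Criterion 6 recognises this for hormones by fixing type and dose, but the rule starts at study entry. A woman who began a hormone or switched steroid a week before baseline meets criteria 5 and 6 simply by staying on it. Her baseline is read before the new regimen has had its effect, and whatever that effect is then falls inside the measured change. A woman who stopped or reduced a therapy just before baseline has the opposite problem: a later loss of control would count against the laser.

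For steroids the protocol itself gives reason to care. Its Background says "The anti-inflammatory properties of clobetasol and other steroids have been most effective in managing associated symptoms", and criterion 4 treats 12 weeks as long enough to judge a steroid. What is at stake is whether the primary result can be attributed to the device.

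**Working it through.** The plan gives no figure on this point to reproduce. The check sets the rules side by side, then the timing, then a range on stated assumptions.

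**1. What the criteria cover**

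| Therapy | Unchanged before baseline | Continued in study | Type and dose constant in study |
|---|---|---|---|
| Topical steroid (item 5) | not required | required | not required |
| Hormone (item 6) | not required | required | required |

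**2. Whether criterion 4 closes the gap**

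- No response over 12 weeks: a woman who has only just started her first steroid cannot enter this way. One who failed a course and then restarted, switched or stepped up can, because the failed regimen need not be the one in use at baseline.
- Lack of control on maintenance therapy: no duration is given, and nothing rules out a recent adjustment.
- Refusal: ordinarily there is no new steroid to carry in, although one stopped recently is possible.
- Hormones: not mentioned.

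The protection is partial for steroids and absent for hormones.

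**3. Timing**

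Inputs: up to 5 treatments, 4±1 weeks apart (Synopsis); first follow-up 6±2 weeks after the last (Study Duration and Timelines). For k treatments, the weeks from treatment 1 to the first follow-up are (k−1)(4±1) + (6±2).

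- k = 5: nominal 4×4+6 = 22; range 4×3+4 = 16 to 4×5+8 = 28
- k = 4: nominal 18; range 13 to 23
- k = 3: nominal 14; range 10 to 18
- k = 1: nominal 6; range 4 to 8

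With four or five treatments, a steroid changed just before baseline has passed the protocol's own 12-week period before the first primary reading. With fewer it may not have done so by then, but the 6- and 12-month readings lie beyond 12 weeks in every case.

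**4. Size, on assumptions**

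Let p be the net share of women with a recent change in one direction and d its own effect on the item. The shift in mean change is p×d, with the sign of the direction. The documents give neither value. Assume p = 0.10-0.30 and d = 0.5-1.0 point on a 5-point item:

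- Women: 45×0.10 = 4.5 to 45×0.30 = 13.5, about 5 to 14
- Shift: 0.10×0.5 = 0.05 to 0.30×1.0 = 0.30 point, upward after net step-ups and downward after net step-downs
- Against an assumed 1-point improvement: 5% to 30%

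**5. Consequence for a test, on assumptions**

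Assume a one-sample test of mean change, two-sided 0.05, normal approximation, n = 45, no laser effect, all recent changes upward, and d now in SDs of change. Then P(significant improvement) = 1 − Φ(1.96 − p·d·√45), against 2.5% in that direction with no shift.

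- p = 0.1, d = 0.3: 3.9%
- p = 0.2, d = 0.5: 9.9%
- p = 0.3, d = 0.5: 17.0%
- p = 0.3, d = 0.8: 36.3%

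A net downward shift would instead hide part of a real effect.

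**6. Cost of a restricted analysis**

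If 14 of 45 are flagged, 31 remain, and the interval widens by √(45/31) = 1.20, about 20%.

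**The case against.** The strongest reply is that this population is chosen for steroid failure or refusal. Known non-responders are the women least likely to gain from another topical steroid, and the Background's statement on steroid efficacy describes patients with the disease in general. This stands as a reason to expect a smaller d for steroids, and nothing in the documents says how common a switch or step-up after failure is. It does not remove the gap: a change of potency or regimen after failure is permitted, and hormones have no such filter.

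Four stronger readings are tempting and are not supported.

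- A reader might infer that a recent therapy's effect will be reported as laser efficacy. The documents show only that the design cannot tell the two apart. A recent stop or reduction works the other way. The architectural component is probably less exposed, since the Background credits steroids with preventing scarring and does not claim reversal.
- A reader might infer that hormones are known to act on the scored items. The Background does not list hormones among treatments, and the 12-week period concerns steroids. The only hint is that criterion 6 fixes hormone type and dose.
- A reader might infer that criterion 5 already holds the steroid regimen constant. It requires continuation and nothing more.
- A reader might infer that the 6-month medication list is unused. It is part of the history taken to establish eligibility; what is missing is a recent-change threshold attached to it.

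It is also fair to say that a with-and-without analysis is commonly left to the statistical analysis plan, and that the case report form, which is not shown, may already hold dates. The eligibility rule itself, however, belongs in the protocol.

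**Conclusion.** The point holds as a possible confounding of unknown size and direction. The protocol sets no period of unchanged steroid or hormone therapy before baseline. Criterion 4 protects only in part, and a single-group change from baseline offers no other way to separate a recent therapy change from the laser.

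The wording of the criteria and the 16-28 week timing for five sessions come straight from the document. The 0.05-0.30 point range and the test probabilities rest wholly on assumed shares and effects; they show what the gap could do and are not estimates for this trial. If few women change therapy before entry, or if non-response to steroids carries over to later regimens, the effect is small. The change is worth making because it is cheap and protects the attribution of the primary result.

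**What to change.** Give criterion 5 the type-and-dose constancy wording that criterion 6 already has. In both criteria, require the regimen to have been unchanged for a fixed lead-in before the baseline reading. The sponsor sets and justifies the length; keeping it within the 6 months of the medication list lets that list serve as the check. A rule on change in either direction covers starts, switches, step-ups, reductions and stops alike.

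If entry is not to be restricted, record the start date and last-change date for each steroid and hormone, unless the case report form already does so. Flag women with a change inside the lead-in, and report the primary change with and without them as a sensitivity analysis.

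The first route costs a phrase in two criteria and the deferral of a few women until they are stable. The second costs at most two date fields and one extra table, with a restricted analysis whose interval is about 20% wider if 14 of 45 women are flagged.
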